6.0 Expected Risks/Benefits

Potential Risks. There is minimal likelihood or seriousness of potential risks to participants. There are no identified physical, legal, or financial risks. Participants may become fatigued during completion of the study questionnaires and HRV monitoring and may feel apprehensive or distressed sharing information, but there is low probability of this and a low level of seriousness. There is potential for loss of confidentiality; however, procedures to protect against this risk will be put in place, as described below. Patients will continue to seek and receive standard medical care for their IHD diagnosis; therefore, any health care problems that may arise will be referred to their health care provider.

Protections Against Risk: The PI who will conduct remote data collection (by phone) 2 weeks after patients' hospital discharge, has been trained to assess for potential fatigue or apprehension of participants. If participants exhibit apprehension, they will be given the option to discuss this, to complete the questionnaires at another time, to be referred to their physician for further counseling follow-up, or to discontinue the study. These are all expected to be effective approaches. Patients will additionally be informed that they can withdraw from the study at any time, without loss of benefits they would otherwise be entitled to and without penalty to their health care. There is no risk for incidental findings.

7.0 Data Collection and Management Procedures

The Polar H7 heart rate monitor connects to the ActiGraph with *Bluetooth*[®] wireless technology so that the interval between normal heart beats (RR data) can be transferred to comma-separated value files for HRV analysis. The RR data will be exported from ActiLife and uploaded and analyzed in Kubios HRV Software (a secure HRV analysis software for scientific research) to generate the time, frequency, and nonlinear domain measures of HRV. Patient numeric codes will be used when analyzing the data; no patient identifiers will be used. All questionnaire and electronic medical record data will be logged directly into the REDCap database via Web interface. The web server synchronizes uploaded files to an alternate location and is backed up daily. De-identified data sets for analyses will be created by importing data from REDCap into the statistical programs R and SPSS.

8.0 Data Analysis

Data Analysis for Each Aim. Confirmation of the internal reliability of scales will be assessed using Cronbach's alpha. The following analyses will be used for each aim.

Aim 1: Kubios HRV software will be used to generate the HRV data for time, frequency, and nonlinear domain analyses. Kubios uses a threshold-based artifact correction algorithm that compares RR beats against a local average interval. The lowest level threshold that accurately detects artifact without overcorrecting normal beats will be used for each recording. Recordings with >5% artifact will not be used in analysis because even a small number of corrected ectopic or missing beats can have a great influence on short-term HRV results. To prevent the issue of not having useable data for a participant, participants are instructed to obtain the measurement at two separate timepoints. The recording with the least artifact will be used. The primary analysis for Aim 1 involves regressing hopelessness levels on HRV, after controlling for relevant demographic (e.g., age, sex) and other covariates (e.g., time of day, deviation from protocol,

etc.), using a multiple regression framework. All covariates as well as hopelessness and HRV levels will be normalized using transformations as needed; to ensure model robustness to variable distributions we will also apply rank-based approaches and bootstrapping of standard errors. As part of a sensitivity analysis, we will fit these same models within the two subgroups: those with moderate to severe hopelessness versus minimal to no hopelessness. Additional subgroup analyses will be completed to evaluate potential differences between sexes and type of IHD event and will include adding interaction terms to the models between sex or type of IHD event and HRV.

Aim 2: The STHS and ESSI scores for all patients in [name] study enrolled until 3/6/23 and the 45 patients that will be recruited for the proposed application will be pooled to assess the relationship between hopelessness and PSS. Again, we will analyze the relationship using a multiple regression framework regressing STHS on ESSI and controlling for relevant demographics (see previous paragraph). A secondary analysis will add depression to the model to ensure that any relationship between STHS and ESSI is not better explained by depression. Additional secondary analyses will follow as noted above with subgroup analyses by level of hopelessness and interactions for sex and type of IHD event with ESSI.

Aim 3: Finally, we will follow the approach of Shrout and Bolger to evaluate the potential for HRV to be acting as a mediator of the PSS and hopelessness relationship. As suggested by Shrout and Bolger, bootstrapping will be used to determine the significance of the mediation effect.

Missing Data. Previous analyses using several of the same instruments in similar populations have yielded low missing data rates (< 1-2%). These individuals are typically not included in the analysis. For scales such as the STHS and PHQ-9, a regression-based imputation procedure to predict single or multiple missing items will be used, assuming data are missing completely at random.

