Heart Rate Variability Procedures. At Week 2, participants will be instructed to place the Polar H7 heart rate monitor around the center of their chest, in contact with the skin, and the ActiGraph wGT3X-BT around their waist, according to directions outlined in the written instructions provided and as demonstrated in the instructional video and practiced with the applicant over the phone. Participants will be informed that the monitors are used to gather data about their body at rest. The Polar H7 heart rate monitor connects to the ActiGraph with Bluetooth® wireless technology so that the interval between normal heart beats (RR data) can be transferred to csv files for analysis. The HRV protocol will take place during a 10-minute time period on two consecutive days, to ensure at least one 10-minute time frame of usable data. Participants will be instructed to place the monitors first thing in the morning after they wake up and empty their bladder. Once the monitors are placed, participants will be instructed to lay supine quietly for 10 minutes and avoid moving or using any devices or watching tv. The standardized HRV protocol improves reliability of the HRV measurement because control of extraneous variables is maintained. Respirations will not be controlled because this can artificially increase HF HRV. The gold standard amount of time for a short-term HRV recording is 5 minutes. The 5 minutes of the recording with the least amount of artifact will be used for analysis. After 10 minutes of recording are completed, the heart rate monitor and ActiGraph will be removed. After the participant completes the 10-minute HRV measurements on two consecutive days, they will be asked to return the monitors in a prepaid envelope that will be

picked up from their mailbox by USPS and returned to the PI, mitigating any exposure to COVID-19.

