9.0 Quality Control and Quality Assurance

The PI is responsible for collecting and analyzing the data for the proposed study. HRV data will be analyzed as soon as monitors are returned to ensure proper data capture. Participants that do not have an appropriate HRV recording will be asked to wear again. The PI will ensure all data is entered accurately during each visit.

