Appendix C

Participant Documents

C1: Written Instructions to Complete Heart Rate Variability Measurement

Placement of Two Monitors

Thank you for your participation in our research study. When you receive this package, please give me a call and I will instruct you on how to wear the monitors for the study. The instructions below describe the same process I will guide you through over the phone.

Please complete your wearing of the two monitors the first time on the morning after you receive the package. We ask that after you wake up, use the restroom, and then place the monitors and wear them for 10 minutes. In the bag you will find the two monitors. The monitor labeled Polar will need to be worn around your chest and in contact with your skin. Please open the ultrasound gel in the bag and place some on the inside part of the Polar monitor. This helps it connect better with your skin. Next, place the monitor around your chest and make sure it is tight enough so that it does not move. The piece that has Polar written on it should be in the front center of your chest. Next, place the red monitor around your waist. The two monitors should be worn as shown in the image below. A blue light should flash on the red activity monitor when both monitors are on correctly. If a blue light is not flashing, use your hands to warm the monitor around your chest until the blue light flashes.

Once both monitors are on correctly, please find a spot in your house where you feel comfortable lying flat on your back for 10 minutes, such as your bed or a couch. While lying down, please remain silent and try not to move for the 10 minutes. Once the 10 minutes is done, you can remove both monitors.

Complete this same process again the next morning. After you have worn the two monitors two times for 10 minutes, you can remove them a final time and place them in the prepaid return envelope.

[figure not shown]

Figure showing proper monitor placement.

Thank you!

C2: Directions to Return Monitors after Heart Rate Variability Measurement

Directions to Return 2 Monitors to Research Staff

After you have worn the 2 monitors for 10 minutes on two consecutive days and completed your phone visit with a data collector, please place the monitors in the return envelope. Shipping has been prepaid and the US Postal Service will pick up the envelope from your mailbox.

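### The artifact-correction threshold for HRV is chosen recording by recording, with no numeric criterion and no masking to hopelessness group, which risks differential measurement in Aims 1 and 3

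*Combined protocol and SAP*

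**What the plan says.** Section 8.0 (Aim 1) describes a threshold-based Kubios algorithm and then the rule for setting it: "The lowest level threshold that accurately detects artifact without overcorrecting normal beats will be used for each recording". Three further choices rest on the artifact count:

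- exclusion: "Recordings with >5% artifact will not be used in analysis" (Section 8.0), justified because "even a small number of corrected ectopic or missing beats can have a great influence on short-term HRV results";
- choice between the two days: "The recording with the least artifact will be used" (Section 8.0);
- choice of segment: "The 5 minutes of the recording with the least amount of artifact will be used for analysis" (Section 5.0).

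On who does the work and when, Section 9.0 says: "The PI is responsible for collecting and analyzing the data for the proposed study". It adds: "HRV data will be analyzed as soon as monitors are returned to ensure proper data capture". Section 7.0 provides for numeric codes in place of identifiers during analysis. Section 8.0 also plans rank-based methods, bootstrapped standard errors and, as a sensitivity analysis for Aim 1, the same models within each hopelessness subgroup.

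**The concern.** Kubios applies the threshold, but a person decides which level is accurate enough and which overcorrects. The rule has a direction (the lowest level that works), but its end point is undefined: there is no default level, tie-break, log or second reader. The plan itself says that a few corrected beats can matter a great deal.

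If that choice differs systematically between the hopelessness groups, the difference enters the Aim 1 regression as an HRV-hopelessness association, or cancels a real one. In Aim 3 it enters the mediator. Rank-based methods and bootstrapping deal with distributional shape. They cannot detect a measurement that differs by group.

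**Working it through.** **What the processor knows.** The relevant sections, side by side:

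| Point | Source | What follows |
|---|---|---|
| Every patient in the PI's study screened below 1.8 | Appendix A1 | Group is known by source |
| The PI makes the Week 2 call for these patients | Section 5.0 | The PI takes the score |
| The call script branches on a score of 1.8 | Appendix B1 | The score is worked out during the call |
| Return instruction: "completed your phone visit with a data collector, please place the monitors in the return envelope" | Appendix C2 | The score exists before the HRV data arrive |
| Numeric codes replace identifiers | Section 7.0 | Protects identity; group and score are not stated to be masked |

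This chain is complete for the 45. For parent-study patients the documents state neither who interviews them nor, expressly, who processes their recordings. If Section 9.0 makes the PI the processor, the PI would know their group by source but not necessarily their score. Knowledge of group is enough for a group-wise difference.

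**How far the choice reaches.** The percentage of beats flagged depends on the threshold. The 5% exclusion, the choice of day and the choice of 5-minute segment are objective in form but inherit that choice. The request to wear the monitors again (Section 9.0) may do so too, since an appropriate recording is not defined.

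**Size, for illustration only.** The plan gives no alpha, power or effect size for Aim 1, so there is no figure to reproduce beyond 225 + 45 = 270. Sections 5.0 and 8.0 limit Aims 1 and 3 to parent-study patients who meet this study's criteria, so 225 is an upper bound.

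Assumptions not in the documents: two-sided alpha 0.05; a processing shift of d SD of HRV in one group; group correlates 0.5 to 0.7 with the Week 2 score; no covariates; no true association.

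With p = 45/270 = 1/6, pq = 0.1389. The correlation of group with HRV is r_g = d√(pq) / √(1 + d²pq). The spurious correlation is r = r_g × (0.5 to 0.7). The rejection rate is Φ(z − 1.96) + Φ(−z − 1.96), with z = atanh(r) × √267.

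| d | r_g | Spurious r | False-positive rate |
|---|---|---|---|
| 0 | 0 | 0 | 5% |
| 0.1 | 0.037 | 0.019–0.026 | 6–7% |
| 0.2 | 0.074 | 0.037–0.052 | 9–14% |
| 0.3 | 0.111 | 0.056–0.078 | 15–25% |
| 0.5 | 0.183 | 0.092–0.128 | 32–56% |

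A simulation (4,000 runs per setting; Week 2 scores assumed N(1.5, 0.30) and N(2.1, 0.35)) gives 4.9, 6.6, 9.8, 17.3 and 37.6% for the same shifts. With 45 v 100 it gives 4.8, 6.6, 11.2, 18.3 and 41.7%, so a smaller parent-study contribution changes little.

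The opposite shift hides an effect. With an assumed true r of −0.2 and 45 v 225, simulated power falls from 92% with no shift to 85% at 0.1 SD, 64% at 0.3 SD and 37% at 0.5 SD.

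**The case against.** The strongest reply is that the plan already contains a check aimed at this. A constant between-group shift, which is what the table models, cancels when the Aim 1 model is fitted within each subgroup. That stands, but only in part. It is a sensitivity analysis, one subgroup has 45 patients, it does not remove choices related to the individual score, and none is stated for Aim 3.

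The 5% exclusion and the least-artifact choices of day and segment also limit how much correction is left to argue about. This is fair, although each depends on the threshold.

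A reader might infer three stronger things that the documents do not support:

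- That the PI knows every participant's score. This is documented only for the 45, which is 45/270 = 17% of the maximum sample.
- That the groups are processed in different periods, so that drift in judgement lines up with group. No recruitment dates are given for the 45. Section 11.1 and Appendix A1 describe one screening stream split at 1.8, which suggests at least overlapping enrolment.
- That the final threshold is fixed when the monitors come back. Section 9.0 gives data capture as the purpose of that analysis, and nothing says the analytic threshold is settled then.

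The shift sizes have no basis in the documents, and at 0.1 SD the inflation is small.

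**Conclusion.** The point holds as a risk of bias. An undefined, per-recording choice is made on the key variable of Aims 1 and 3, and nothing in the plan masks the person making it to group. Both group and score are known beforehand for the 45; for parent-study patients it is at most group, and only if the PI processes their recordings.

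The documents do not show that bias will occur, in which direction, or how large it would be. The range from about 7% false positives at 0.1 SD to 25% at 0.3 SD depends wholly on the assumed shift, the assumed group-score correlation and alpha 0.05. With no shift the rate is nominal. The change is worth making because it is simple and uses data the study will already hold.

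**What to change.** 1. Keep the check on monitor return as a pass/fail on data capture, with the pass criterion written down.
2. Do the final HRV processing from the stored RR files under new, script-generated random codes, with both groups mixed in random order and without group or STHS score. Lock the HRV file before merging it with REDCap. State who processes the parent-study recordings.
3. Repeat Aims 1 and 3 with one fixed Kubios threshold for all recordings, as a sensitivity analysis.
4. Tabulate the threshold used and the percent of beats corrected by group.

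Cost: no new data and no extra reader. The pass covers up to 270 × 2 = 540 recordings. At an assumed 3 to 10 minutes each, that is 540 × 3/60 = 27 to 540 × 10/60 = 90 hours if done on top of the planned processing, and less if it replaces it. The fixed-threshold run adds to this. A fixed threshold may overcorrect some recordings, so it should remain a sensitivity analysis.

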9.0 Quality Control and Quality Assurance

The PI is responsible for collecting and analyzing the data for the proposed study. HRV data will be analyzed as soon as monitors are returned to ensure proper data capture. Participants that do not have an appropriate HRV recording will be asked to wear again. The PI will ensure all data is entered accurately during each visit.

10.0 Data and Safety Monitoring

Institutional Review Board (IRB) approval was received from both the sponsoring institution and recruitment site hospital before the study began.

11.0 Regulatory Requirements

11.1 Informed Consent

The recruiting hospital is responsible for recruiting, consenting and screening eligible patients (i.e., those who are screened as hopeless) for [name] study. Interested patients will provide verbal consent for the hopelessness screening, including a HIPAA waiver. The screening consent includes permission for review of the patient's medical records to collect patient

characteristics and comorbidities. Those patients who do not qualify for [name] study will be referred to the PI for assessment of eligibility for the PI's study.

Patients who do not meet the hopelessness criteria for [name] study (they have minimal or no hopelessness) will be approached by the PI to discuss possible enrollment in the proposed study. The PI will screen patients over the phone or in person to ensure they do not meet any of the study exclusion criteria. If a patient is eligible and agrees to enrollment in the study, written consent will be obtained. The consent will explain the study, risks, benefits, voluntary nature of participation, and the patient's right to discontinue participation at any time without consequences. If the participant is enrolled after hospital discharge, they will be sent a link via email or text message, which will take them to the REDCap e-consent page, where they will provide an electronic signature. After the electronic signature is accepted and confirmed, a copy of the signed e-consent will be sent to the patient by email and/or postal mail and a copy will be saved in the REDCap database.

11.2 Subject Confidentiality

Confidentiality: The confidentiality of participants and their data will be protected in the following ways: 1) no identifying information will be used as sources of identification for participants; 2) at time of enrollment, the REDCap system will assign each patient a four-digit numerical code, which will become the identifier of records for all patients; 3) consent forms will be kept double-locked separate from research data; 4) contact information needed for USPS shipments and phone visits will be entered and stored on a secure dedicated server with appropriate firewalls using the REDCap system; 5) all electronic tablets used to collect and send data will be double-password-protected; 6) electronic copies of completed questionnaires will be stored on a secure dedicated server with appropriate firewalls using the REDCap system; 7) dissemination of research data will be done in aggregate form only; and 8) hospital name and city will be omitted in all reports and presentations.

11.3 Unanticipated Problems

Participants will be queried about potential adverse events and unanticipated problems as defined below:

Adverse event. An adverse event will be defined in this research as any untoward or unfavorable medical occurrence in a study participant, including any abnormal symptom (including psychological), sign (including physical), or disease temporally associated with the participant's involvement in the research, whether or not considered related to participation in the research. Adverse events in this study will include, but not be limited to, death, cardiac restenosis (myocardial infarction, revascularization with coronary artery bypass surgery or percutaneous coronary intervention), or suicidal ideation.

Unanticipated problem. An unanticipated problem will be defined in this research as any incident, experience, or outcome that meets all of the following criteria: 1) unexpected (nature, severity, or frequency) given the research procedures that are described in the research protocol and informed consent, and given the characteristics of the study population; 2) related

or possibly related (reasonable possibility that the problem may have been caused by study procedures) to participation in the research; and 3) suggests that the research places participants or others at a greater risk of harm (including physical, psychological, economic, or social harm) than was previously known or recognized. Unanticipated problems in this study will include, but not be limited to, a breach of confidentiality.

Adverse events and unanticipated problems will be monitored in several ways during the implementation of the study protocol. First, adverse events and unanticipated problems will be monitored by the PI during data collection. The PI will document any adverse events and unanticipated problems reported to them by participants and report these immediately to their advisor. Second, all patients will be provided a toll-free phone number to contact the PI directly if they have any issues or concerns to report

All adverse events and unanticipated problems will be reported to the PI's advisor within 24 hours. If the advisor evaluates the adverse events and unanticipated problems to be moderate or serious, she will notify the PI and convene the SMC. All unanticipated problems or serious adverse events that may be related to the study protocol will be reported by the PI to the university IRB and hospital IRB within 48 hours of the committee meeting. The PI will immediately respond and closely monitor any reported adverse events and unanticipated problems. The PI will enter all adverse events and unanticipated problems into the study database. Regardless of whether an adverse event or unanticipated problem is related to the study protocol, the participant's primary care provider will be notified of an event if it affects the patient's clinical status.

APPENDICES

Appendix A	Screening, Recruitment, and Enrollment
A1	Eligibility Screening for Hopelessness
A2	Exclusion criteria for Enrollment in PI's Study
Appendix B	Data Collection Script
B1	Week 2 Data Collection Script
Appendix C	Participant Documents
C1	Written Instructions to Complete Heart Rate Variability Measurement
C2	Directions to Return Monitors after Heart Rate Variability Measurement
Appendix D	Data Collection Instruments
D1	State-Trait Hopelessness Scale
D2	ENRICH Social Support Instrument
D3	Demographic Instrument
D4	Patient Health Questionnaire

